4.7 Sample size and power considerations

As illustrated below, since the INKA trial will include 200 patients in total (approximately 100 individuals in each group), we anticipate that the present study (comparing INKA vs non-INKA participants) will enrol around 400 patients in total; i.e. the enrolment of the “non-INKA participants” (nINKA) will be recruiting individuals during the exact same time period as the INKA trial is enrolling eligible patients, which is estimated to be:

First Patient First Visit (FPFV): 01-02-2022

Last Patient First Visit (LPFV): 01-07-2023

The present study will be focusing on whether the treated (INKA) and untreated (nINKA) subjects have similar distributions of observed baseline covariates. We will assess whether the propensity score model has been correctly specified: comparing mean’s and prevalence’s of baseline characteristics using standardized differences.

[figure not shown]

Figure 2 sample size and power considerations

As illustrated in figure 2, we will tentatively assume that a standardized difference between groups could be indicative of a “significant” difference between the groups.

NOTE: In the INKA trial the primary outcome is the OKS at week 38. For the intensive diet intervention strategy to be worthwhile it needs to demonstrate non-inferiority in the OKS score after 38 weeks compared to KA: The minimally important difference estimate applicable for group comparisons in RCTs has been suggested to be 4.84 OKS points. Therefore, we will consider a difference in group mean OKS scores smaller than or equal to 4 OKS points as showing non-inferiority. Based on a recent observational study on 960 KA patients in our region, a standard deviation of 8 OKS points after 38 weeks is expected. Thus, if the true difference between groups is 0 OKS points in a balanced design (1:1 randomization), a one-sided t-test with a significance level of 0.025 will have a power of 90.3% to reject the null hypothesis that the intensive diet intervention is inferior to KA, with a sample size of 86 patients per group (172 in total). To account for attrition (incl. possible “cross-over”) in the ITT population it is decided to aim for, and randomize, 200 patients in total, which correspond to - based on the above assumptions - a statistical power of 94% to reject the null-hypothesis that intensive diet is inferior to KA. Power and sample size analyses were conducted using ‘proc power’ in SAS (SAS Institute Inc., Cary, 968 North Carolina).

4.8 Bias and confounding variables

Confounding is an important concept in epidemiology, because, if presents, it can cause an over- or underestimate of the observed association between exposure and health outcome. The distortion introduced by a confounding factor can be large, and it can even change the apparent direction of an effect. However, unlike selection and information bias, it can be adjusted for in the analysis.

The challenge with observational data (like the proposed comparison) is that the groups (INKA vs nINKA) are not applied randomly, leading to selection bias and thus potentially confounding variables. For example, when we study the impact entering a “promising weight loss trial” before having direct access to a KA, and we compare the outcome among those (who accept the invitation to join the INKA trial) versus all of those who declined, we would potentially have some selection bias, as those who decline are different per definition. The difference can range from baseline characteristics that would influence the outcome; i.e., an advanced disease stage that make any potential delay of the surgery intolerable, or failure/ineffectiveness of previous weight loss trials. Or it can be a characteristic with neglectable effect on the outcome, ie., not having the time or the desire to be included in a clinical trial. Improved confounding variable balance (i.e. de-confounding) between INKA and nINKA groups can be achieved by matching observations from each group based on the propensity score, which in this case would be the probability that a patient accept participation in INKA given the observed covariates.

4.9 Statistical methods

We will use the term balance diagnostics to describe the methods we use to assess whether the distribution of baseline covariates is similar between the two groups (INKA and nINKA, respectively). We designed the study to compare the mean (or medians) of continuous variables or the prevalence of dichotomous baseline covariates between INKA and nINKA participants. We will report the means and/or medians of continuous variables and the distribution of categorical variables for each of the two groups. These crude comparisons (between INKA=treatment and nINKA=control, respectively) will enable an assessment of the comparability of the two groups which will be indicative of the generalizability of the INKA trial (24).

Standardized differences for comparing means and prevalences between groups: For continuous variables, the standardized difference is defined as

$$d = \frac{(\bar{x}_{\text{treatment}} - \bar{x}_{\text{control}})}{\sqrt{\frac{s_{\text{treatment}}^2 + s_{\text{control}}^2}{2}}}$$

where x 's denote the sample means of the covariate in treated (INKA) and control (nINKA) participants, respectively, while the s^2 's denote the sample variance of the covariate in the groups. For dichotomous variables, the standardized difference will be defined as

$$d = \frac{(\hat{p}_{\text{treatment}} - \hat{p}_{\text{control}})}{\sqrt{\frac{\hat{p}_{\text{treatment}}(1 - \hat{p}_{\text{treatment}}) + \hat{p}_{\text{control}}(1 - \hat{p}_{\text{control}})}{2}}}$$

where p 's denote the prevalence or mean of the dichotomous variable in treated (INKA) and control (nINKA) participants, respectively.

By using the standardised differences, it allows for the comparison of the relative balance of variables measured in different units (e.g. age in years with a 'Timed Up and Go'). Unlike t-tests and other statistical tests of hypothesis, the standardized difference is not influenced by sample size. Thus, the use of the standard difference will be used to compare balance in measured variables between treated and untreated subjects. Standardized differences are increasingly being used to compare balance in baseline covariates between groups in the propensity-score matched samples. A limitation to their use is lack of consensus as to what value of a standardized difference denotes important residual imbalance between treated and untreated subjects in the matched sample. While there is no clear consensus on this issue (24), as illustrated in the figure above, we will apply a standardized difference of ≥ 0.2 to indicate that there might be a meaningful imbalance in the baseline covariate (i.e. possibly poor generalizability); whereas a standardized difference ≥ 0.8 will be considered as definitive incomparability.

We will also apply the PROC NPAR1WAY procedure (using SAS software) to compute empirical distribution function (EDF) statistics, to statistically test the distribution of the baseline variables. PROC NPAR1WAY provides a summary of the Wilcoxon scores for the analysis baseline variable by class level (INKA and nINKA, respectively). It also displays the one-way ANOVA statistic, which for Wilcoxon scores corresponds to the Kruskal-Wallis test: If the statistical test indicates that there might be difference between groups <0.05 this ($P<0.05$) leads to rejection of the null hypothesis that the groups are similar.

The propensity score is the conditional probability that a participant accepts the invitation to participate in the INKA (weight loss vs direct surgery) trial given the participant's observed covariates (i.e. baseline measures). The goal of the propensity scoring will be to evaluate whether the data is comparable between the datasets by enabling a balancing observed covariate between individuals in INKA and nINKA, respectively. We will organise our data into a single dataset with all the baseline (potential confounding) variables that we collect in this study, along with the column that indicates whether the patient accepted participation in INKA (i.e. 1='yes' and 0='No', respectively). From this data matrix, logistic regression will be used to develop propensity scores, represent the probability that a patient accept participation in INKA based on the participant's observed covariates. Thus, we will create a logistic regression model in which the baseline variables are used to balance between our groups are used as our predictors of group, our dependent variable ($y=1$, INKA participation; while $y=0$, nINKA) in the logistic regression model.

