Conflict of interest declaration

None declared.

SUMMARY

Background: Overweight is a main and modifiable risk factor for developing knee osteoarthritis (OA). Studies indicate a beneficial effect of weight loss on the symptoms of knee OA. The Intensive diet vs Knee Arthroplasty (INKA) trial is a RCT, which aims to assess weight loss as a non-inferior intervention and/or an alternative to surgical knee arthroplasty in overweight and obese patients suffering from knee OA. As RCTs carry a risk for selection bias and thereby risk for low external validity, comparison of the recruited trial participants and the invited participants, who decline trial participation will enable assessment of the external clinical validity and generalizability of the INKA trial

Objective: The objective of this study is to compare baseline characteristics of overweight knee OA patients accepting vs. declining enrolment in the INKA trial to explore if enrolled patients differ systematically from the declining participants with respect to both measured as well as unmeasured baseline characteristics.

Design: Cross-sectional study collecting baseline characteristics of patients with Knee OA eligible for enrolment in the INKA trial, whether accepting or declining enrolment.

Setting: Potential trial participants will be identified during their routine visits in the orthopaedic outpatient clinics at Copenhagen University Hospital Bispebjerg-Frederiksberg and Copenhagen University Hospital Amager-Hvidovre.

Participants: Adults ≥ 18 years old, obese ($BMI \geq 30 \text{ kg/m}^2$), with an indication for primary knee arthroplasty (unicondylar or total arthroplasty) due to knee OA are included either with consent or refusal to participation in the INKA trial. We will recruit 400 patients in total, 200 in each group.

Measurements: Baseline characteristics for the 2 groups are obtained extracting data from the participants' medical records including questionnaires answered by all patients, of which the main is The Oxford Knee Score (the primary outcome for INKA participants).

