4.3 Participants

All patients found eligible in INKA study (inclusion criteria for INKA) and accepting and declining enrolment in the INKA study are invited to participate in our study. We report the number of patients assessed for eligibility and reasons of exclusion. Study participants will be adults (i.e. at

least 18 years old), have a diagnosis of knee osteoarthritis with an indication for primary knee arthroplasty (unicondylar or total arthroplasty), and be obese ($BMI \geq 30 \text{ kg/m}^2$). An individual will be eligible for study participation if he/she meets the following criteria:

1. Age 18 or more
2. A clinical and radiological diagnosis of knee OA
3. $BMI \geq 30 \text{ kg/m}^2$
4. Motivated for weight loss as by the provided program
5. Signed informed consent.

A possible participant will, however, be excluded from the study if he/she meets any of the following criteria:

1. The scheduled surgery is for revision of an existing prosthesis
2. Planned surgery for more than one knee within the observation period
3. KA indication due to sequelae of fracture(s)
4. Injection of medication or substances in the target knee within 3 months prior to participation
5. Immuno-inflammatory arthritis as cause of the knee OA
6. Current systemic treatment with glucocorticoids equivalent to $> 7.5 \text{ mg}$ of prednisolone/day
7. Previous or planned obesity surgery
8. Inability to understand or read Danish incl. instructions and questionnaires
9. Any other condition or impairment that, in the opinion of the investigator (or his/her delegate), makes a potential participant unsuitable for participation or which obstruct participation.

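### Does judging generalisability from acceptors versus decliners, without the acceptance rate, overstate how far the INKA sample departs from eligible patients?

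*Combined protocol and SAP*

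**What the plan says.** The Summary and section 3.0 set the objective as a comparison of baseline characteristics between patients who accept INKA and patients who decline. Section 2.0 gives the reason: judging generalisability requires a look at excluded and declining patients.

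Section 4.9 defines d for continuous and dichotomous covariates between INKA and nINKA, and says the crude comparisons "will enable an assessment of the comparability of the two groups which will be indicative of the generalizability of the INKA trial". It sets two cut-offs. At 0.2 or more, "there might be a meaningful imbalance in the baseline covariate (i.e. possibly poor generalizability". At the upper end, "a standardized difference ≥ 0.8 will be considered as definitive incomparability". It concedes that there is no consensus on what size of difference matters. The distribution tests and the propensity model use the same two groups. Acceptors are not compared with all eligible patients, and the acceptance rate does not enter the analysis.

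On size, the Summary says "We will recruit 400 patients in total, 200 in each group", and section 4.7 expects that the study "will enrol around 400 patients in total". On denominators, section 4.3 says "We report the number of patients assessed for eligibility and reasons of exclusion". Table 1 (section 4.4) has a row for total number and percentage by group, and section 7.0 lists a screening log.

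**The concern.** Trial results are often generalised to everyone who was eligible, and that population contains the acceptors themselves. The more patients accept, the closer the trial sample lies to it, whatever the gap to the decliners. A fixed cut-off on the acceptor–decliner gap gives the same reading at 10% acceptance as at 90%. If both labels in section 4.9 were verdicts on departure from the eligible population, the plan could issue its strongest negative label when that departure is trivial. INKA's external validity would then be marked down for no good reason. External validity is the purpose of the study, so the point deserves a check.

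**Working it through.** **Inputs.** Cut-offs 0.2 and 0.8 (section 4.9). Planned groups 200 and 200 (Summary; section 4.7 gives about 400 in total). The acceptance rate a is not stated. The split implies a = 200/400 = 0.50 if all decliners consent to this study; otherwise a is an assumption and is ranged. The plan calculates no figure on this point: the power figures in section 4.7 concern the parent trial's non-inferiority test and have no bearing here.

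**Step 1, the identity.** Mean(eligible) = a × mean(acceptors) + (1 − a) × mean(decliners). Hence mean(acceptors) − mean(eligible) = (1 − a) × [mean(acceptors) − mean(decliners)]. In within-group SD units the departure is (1 − a)d. This part of the concern is correct.

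**Step 2, departure when d = 0.8 (within-group SD).**

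| a | (1 − a) × 0.8 |
|---|---|
| 0.20 | 0.64 |
| 0.50 | 0.40 |
| 0.70 | 0.24 |
| 0.75 | 0.20 |
| 0.80 | 0.16 |
| 0.90 | 0.08 |

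**Step 3, at the planned split.** With a = 0.50, d = 0.8 and equal within-group variances of 1, the eligible-population variance is 1 + 0.5 × 0.5 × 0.64 = 1.16. The departure is:
- 0.40 in within-group SD units;
- 0.40/√[(1 + 1.16)/2] = 0.385 with the plan's own formula applied to acceptors versus all eligible;
- 0.40/√1.16 = 0.371 in eligible-population SD units.

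Variance ratios (acceptors to decliners) from 1/4 to 4 keep the plan-formula value between 0.34 and 0.45. Dichotomous covariates with decliner prevalence 0.1 to 0.5 give 0.35 to 0.42. All are well above 0.2.

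**Step 4, what would be needed to fall below 0.2.** (1 − a) × 0.8 < 0.2 requires a > 0.75. With the plan's formula the threshold is 74.2%, and with the eligible-population SD 73.5%. Against 200 acceptors that means fewer than 200 × 0.25/0.75 = 67 to 200 × 0.265/0.735 = 72 decliners, where the plan expects 200. Strong variance inequality moves the threshold somewhat: with acceptor variance four times decliner variance, the plan-formula departure is 0.197 at 70% acceptance. None of this brings it near 50%.

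**Step 5, chance.** At a = 0.50 a departure of 0.2 corresponds to a true d of 0.4. With 200 per group, SE = √(2/200 + 0.4²/800) = 0.101, so observing 0.8 or more lies (0.8 − 0.4)/0.101 = 3.96 SE away, a probability of about 0.00004.

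**Step 6, direction of the uncertainty in a.** Decliners must also sign consent for this study (sections 4.3, 5.1, 5.2). Those who refuse are missing from nINKA, so true acceptance would be below the observed share. The factor 1/(1 − a) then shrinks, for example from 2.0 at 50% to 1.25 at 20%.

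**Step 7, what the alternative column would add.** In within-group SD units it multiplies every covariate's d by the same (1 − a), so the ranking of covariates is unchanged. Keeping 0.2 on that scale at a = 0.50 raises the effective cut-off on d to 0.2/0.5 = 0.4.

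**Step 8, the labels.** The generalisability wording is attached to 0.2 only, and it is hedged. The 0.8 wording concerns comparability, and the two things compared are acceptors and decliners. For that statement d is the right quantity and needs no rescaling.

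**The case for a change.** The best counter-argument is that external validity is the declared purpose, that section 4.9 itself attaches a generalisability reading to a numerical cut-off, and that this reading ignores a quantity on which departure from the eligible population depends. At 50% acceptance the 0.2 flag fires when that departure is only 0.10. Nor do the planned outputs guarantee the acceptance rate: section 4.3 names numbers assessed and reasons for exclusion, not the count of eligible patients who declined, and the percentage row in Table 1 gives shares of study participants.

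The arithmetic stands, and so does the remark on reporting: stating the acceptance rate beside Table 1 would help readers, and the eligibility counts and screening log are the natural source. The rest depends on fixing the target population as acceptors and decliners pooled, which no section does. Whether INKA results carry over to patients like those who declined is an equally legitimate external-validity question, it is the one posed in sections 2.0 and 3.0, and for it the acceptor–decliner d is the direct measure. An early flag on a screening criterion worded as a possibility is not a wrong verdict.

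**Conclusion.** The concern does not hold. The factor 1/(1 − a) is correct but applies to a contrast the plan does not set out to estimate; the planned d answers the plan's own question. The feared result, the strongest label alongside a departure below 0.2, needs acceptance above about 73–75% with equal variances. Nothing in the documents points to such a rate: the 200:200 plan gives 0.37–0.40, and non-consenting decliners would push the departure higher. It also requires reading the 0.8 label as a generalisability verdict and moving the 0.2 cut-off to a scale for which it was not set. These figures assume that 200:200 reflects acceptance among eligible patients; the documents do not state the rate. What remains is a reporting preference, with no error in the analysis.

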4.5 Data sources/measurements

4.5.1 The Oxford Knee Score (Primary Outcome)

The Oxford Knee Score (OKS) is a 12-item Patient Reported Outcome questionnaire developed specifically to assess the patient's perspective on the outcomes of knee arthroplasty (KA) with respect to combined pain and physical function. Standardized answer options are given (5 Likert boxes) and each question is assigned a score from 0 to 4. Thus, a total score is calculated that ranges from 0 and 48, with 48 indicating the best outcome. The OKS is short, practical, reliable, valid, and sensitive to clinically important changes over time (16).

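### Is the 0.2 standardized-difference cut-off mis-set for the Oxford Knee Score, given the 4.84-point minimally important difference quoted in the same document?

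*Combined protocol and SAP*

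**What the plan says.** Section 4.9 uses one pair of cut-offs for every covariate. At the lower end, a standardized difference of 0.2 or more is taken "to indicate that there might be a meaningful imbalance in the baseline covariate (i.e. possibly poor generalizability"; at the upper end, "whereas a standardized difference ≥ 0.8 will be considered as definitive incomparability". The same paragraph concedes that the literature has not settled on a value. The standardized difference is not the only tool. Section 4.9 also plans group means and/or medians, Wilcoxon and empirical-distribution-function tests judged at P<0.05, and a propensity model built on all baseline variables.

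The OKS has a special place. The Summary lists the questionnaires, "of which the main is The Oxford Knee Score (the primary outcome for INKA participants", and the heading of section 4.5.1 marks it as the primary outcome.

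The OKS figures in points come from a note in section 4.7 that describes the INKA trial itself: "The minimally important difference estimate applicable for group comparisons in RCTs has been suggested to be 4.84 OKS points"; "we will consider a difference in group mean OKS scores smaller than or equal to 4 OKS points as showing non-inferiority"; and "a standard deviation of 8 OKS points after 38 weeks is expected". Section 3.0 states the aim of the present study as exploring whether enrolled patients differ systematically from decliners.

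**The concern.** The document holds OKS-specific figures and section 4.9 uses none of them. On the SD of 8, the lower flag is 1.6 points, well below the quoted minimally important difference. The upper cut-off is 6.4 points, above it. A gap equal to the minimally important difference would therefore usually get the same hedged label as a gap one third its size.

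No confidence interval for the OKS difference and no equivalence limit is planned, although 200 patients per group would give a precise estimate. Section 2.0 speculates that decliners have worse knees, and the OKS bears directly on that. If the objection held, the study could raise or not raise a flag on its main variable but never show that the groups are alike, and small gaps would count against INKA's generalizability without good reason.

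**Working it through.** **Inputs.** Cut-offs 0.2 and 0.8 (section 4.9); minimally important difference 4.84, margin 4 and SD 8 at week 38 (section 4.7 note); 200 patients per group (Summary). No baseline SD is given, so 8 is an assumption here, and 6 to 10 is used as a range. Probabilities in steps 4 and 5 use the normal distribution with the SD taken as known.

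**1. The plan's own figure.** INKA's non-inferiority power follows from a noncentral t distribution with noncentrality 4 / (8 × √(2/n)).
- n = 86 per group: noncentrality 3.28, power 90.3%.
- n = 100 per group: noncentrality 3.54, power 94.0%.

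Both match section 4.7. The check also shows what the 4 points are: a margin for a one-sided test of a randomised treatment effect at week 38.

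**2. Cut-offs in OKS points** (cut-off × SD).

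| SD | 0.2 SD | share of 4.84 | 0.8 SD | 4.84 in SD | 4 in SD |
|---|---|---|---|---|---|
| 6 | 1.2 | 25% | 4.8 | 0.81 | 0.67 |
| 8 | 1.6 | 33% | 6.4 | 0.605 | 0.50 |
| 10 | 2.0 | 41% | 8.0 | 0.48 | 0.40 |

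The conversion behind the concern is correct. Whether a 4.84-point gap reaches the upper band depends on the SD: at SD 6 it does.

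**3. Precision.** SE = 8 × √(2/200) = 0.80 points. The 95% half-width is 1.966 × 0.80 = 1.57 points (1.18 to 1.97 for SD 6 to 10).

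**4. What the flag does at SD 8.**
- Groups truly equal: the chance of an observed gap of at least 1.6 points in either direction is 2 × (1 − Φ(1.6/0.80)) = 4.6%.
- True gap 4.84: the chance of a flag is Φ((4.84 − 1.6)/0.80) = Φ(4.05), over 99.9%.
- True gap 4.84: the chance of reaching the upper band is 1 − Φ((6.4 − 4.84)/0.80) = 1 − Φ(1.95), about 3%.

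So equal groups are seldom flagged, and a gap of 4.84 points is practically never missed. It is reported with the weaker of the two labels.

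**5. What a ±4-point rule would do at SD 8.** The 95% interval lies within ±4 when the observed gap is at most 4 − 1.57 = 2.43 points. That happens in 99.8% of studies if the true gap is 0, 85% if it is 1.6, and 2.5% if it is 4. The precision is there. But an observed gap between 1.6 and 2.43 points (0.20 to 0.30 SD) would be flagged under section 4.9 and called comparable under the new rule. At a true gap of 1.6 the chance of this is Φ((2.43 − 1.6)/0.80) − Φ(0) = 0.85 − 0.50 = 0.35. In the same zone the 95% interval excludes zero, so the retained P<0.05 test would generally reject similarity too.

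**6. What can be recovered from the planned report.** With equal groups and means reported, the root-mean-square SD is the gap divided by d, and the half-width is 1.966 × SD × √(2/200). For a gap of 1.6 and d = 0.2, the SD is 8 and the half-width 1.57. This is imprecise when d is near zero, and it fails if only medians are given.

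**The case for a change.** The strongest counter-argument is that section 4.9 promises an assessment of comparability, and neither an unraised flag nor a non-significant test is evidence that groups are alike. The two also overlap: at 200 per group an observed d of 0.2 corresponds to t = 0.2/√(2/200) = 2.0, close to the 5% threshold, so for OKS the flag and a mean-based test largely repeat each other. A confidence interval set against a stated limit would support a positive conclusion, and step 5 shows that the sample could deliver one. With only 100 decliners the half-width is still 1.93 points and the chance of an interval within ±4, for equal groups, 97%.

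The logic about absence of evidence stands, and so does the precision. What does not stand is the claim that the document already supplies the limit. The 4-point figure is for a treatment contrast after 38 weeks. Nothing in the document says that a smaller baseline gap between accepters and decliners is trivial. A mean shift smaller than a minimally important treatment effect can still reveal systematic selection, which is what section 3.0 sets out to explore. Nor is OKS judged by the cut-offs alone, since the distribution tests and the propensity model also apply to it.

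**Conclusion.** The concern does not hold. Its arithmetic is right: 0.2 SD is 1.6 OKS points at SD 8, or 1.2 to 2.0 points for SD 6 to 10, always well below 4.84. The inference from it fails for three reasons. The lower cut-off is worded as a possibility and serves as a low-threshold screen that errs towards caution. The 4.84 and 4-point figures answer a different question, in a different comparison and at a different time point. And the study sets out to explore differences, so lacking an equivalence rule is not a failure against its own objective. Adding a ±4-point rule would be a contestable choice: it would treat gaps approaching 0.5 SD (0.67 SD at SD 6) as comparable and would contradict the retained flag in about 35% of studies at a true gap of 1.6 points.

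What is left is a reporting preference, the OKS difference in points with a 95% interval, which corrects no stated figure or rule. The size estimates assume that the week-38 SD of 8 is near the baseline SD and that 200 decliners supply a complete OKS. Figure 2, to which section 4.9 refers for the cut-offs, is not reproduced in the text reviewed, so any rationale given there could not be checked.
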